8.1 Informed Consent

The investigator will provide for the protection of the subjects by following all applicable regulations. These regulations are available upon request from the sponsor. The ICF must be reviewed by the sponsor and approved by the IRB/IEC/REB.

Before any procedures specified in the protocol are performed, a subject must:

- Be informed of all pertinent aspects of the study and all elements of informed consent
- Be given time to ask questions and time to consider the decision to participate
- Voluntarily agree to participate in the study
- Sign and date an IRB/IEC/REB approved ICF

8.2 Subject Demographics/Other Baseline Characteristics

Subject demographic and Baseline characteristic data to be collected on all subjects include: date of birth, gender, and race/ethnicity.

8.3 Medical History

The investigator will perform a comprehensive history at the Screening visit. Significant medical history (at any time) and any medical history within the past 6 months including ongoing medical conditions at the time of signing of the ICF will be recorded. In addition, subject's history of prior CABP will be captured and the following:

- Predisposing factors that may affect lung function (eg, prior lung infection, mild to moderate COPD, symptomatic asthma with wheezing, history of smoking, chronic cough with and without sputum production, etc.).
- Cardiovascular disease and risk factors
- History of pneumococcal vaccination (eg, Pneumovax, Prevnar 13).
- All systemic antimicrobials from onset of the infection will be recorded under concomitant medications.

Where possible, diagnoses are to be recorded. Any event or change in the subject's condition or health status occurring after signing the ICF will be reported as an AE.

8.4 Physical Examination

At Screening, a full physical examination will include the examination of general appearance, skin, neck (including thyroid), eyes, ears, nose, throat, lungs, heart, abdomen, back, lymph nodes, extremities, and vascular and neurological systems.

Information for all physical examinations must be included in the source documentation at the study site. Significant and relevant findings that are present prior to the start of test article must be included in the subject's eCRF. Relevant findings that are present prior to the start of test article must be included in the relevant medical history/current medical conditions screen on the subject's eCRF. Significant findings made after the start of test article which meet the definition of an AE must be recorded on the AE screen of the subject's eCRF.

8.5 Vital Signs

Vital signs include blood pressure (BP), heart rate, pulse oximetry, RR, and body temperature.

• Blood pressure and heart rate should be measured within 30 min before, and approximately (± 15 minutes) 1 hour after the completion of the first dose.

The subject's BP and heart rate should be captured after at least 5 minutes (+ 5 minutes) of rest while in a non-standing position (supine or semi-recumbent, head of bed from 0° to 90°). Subsequent vital sign measurements should be captured in the same non-standing position.

Systolic and diastolic BP will be measured using an automated calibrated device, with an appropriately sized cuff.

A pulse oximeter should be used to capture oxygen saturation.

Heart rate will be measured using an automated calibrated device, when available. If not available, heart rate will be measured manually.

Temperature will be obtained using an electronic (rapid reading) device whenever possible.

8.6 Height and Weight

Height and body weight will be collected.

8.7 Assessment of CABP Symptom Severity

The investigator will specifically assess the presence and severity level of the subject's symptoms of cough, sputum production, pleuritic chest pain, and dyspnea on a 4-point scale (absent, mild, moderate, or severe) based upon the Community Acquired Bacterial Pneumonia Subject Symptom Severity Guidance Framework for Investigator Assessment (see Appendix 3) and enter the symptom severity level into the eCRF. Subjects must have at least 3 of these 4 symptoms of CABP to be eligible for randomization in the study.

8.8 Radiologic Evaluation of Pneumonia

A CXR or CT scan will be obtained for all subjects at Screening (within 48 hours prior to the first dose of test article, see Inclusion Criterion 7). These studies may be obtained as part of routine, non-study evaluation of a subject presenting with signs and symptoms of CABP and therefore may be performed in some circumstances before informed consent is obtained for participation in this study. If a CXR or CT scan is obtained during the course of therapy or during the study period up to the Final Follow-up assessment, the results of the study will be collected. Radiologic evaluation(s) will be performed locally and interpreted by appropriately qualified personnel who are certified or licensed to interpret chest radiographs according to applicable regional requirements, reviewed by the investigator or qualified personnel and the conclusions of this review will be the basis for subject inclusion. The review report should be included in the source documents.

8.9 PORT Risk Class

All subjects who are being screened for the study will have their PORT Risk Class assessed at the Screening evaluation only (see Appendix 4). All subjects must have disease characterized as PORT Risk Class of II or III at randomization.

8.10 Clinical Laboratory Tests

All laboratory testing will be performed by the local laboratory at each site. The relevant local laboratory results from Screening will be used to assess eligibility as per the inclusion/exclusion criteria.

8.10.1 Hematology and Serum Chemistry

Blood testing will include the hematology and serum chemistry parameters as shown in Table 1 and Table 2, respectively. These results for the study timepoints indicated in Appendix 1 will be recorded in the eCRF.

Hematocrit	White blood cell differential (as % cell counts)	
Hemoglobin	-Neutrophils	
Mean cell volume	-Lymphocytes	
WBC count	-Monocytes	
Platelet count	-Eosinophils	
	-Basophils	

Table 1Hematology

Blood glucose	ALT	LDH
Urea	AST	СК
Creatinine	AP	Calcium
Sodium	Total bilirubin	Phosphate
Potassium	Total protein	Cholesterol
Chloride	Magnesium	Uric Acid
Bicarbonate	Albumin	GGT
		Amylase
		Lipase

Table 2Serum Chemistry

ALT = alanine aminotransferase; AST = aspartate aminotransferase; AP = alkaline phosphatase;

LDH = lactate dehydrogenase; CK = creatine phosphokinase; GGT = gamma-glutamyl transpeptidase.

8.10.2 Pregnancy Assessment

All female subjects will have a local laboratory urine or serum pregnancy test at Screening. Results are required for eligibility and will be retained in source documents but will not be entered in the eCRF. If a positive urine or serum pregnancy test result is obtained during Screening, the subject is not to be enrolled.

Should a positive pregnancy test be reported after a subject is enrolled, test article administration should be discontinued (see Section 8.18.6).

8.10.3 Urinalysis

A urine dipstick test will be performed at the local laboratory at Screening, which will include (at minimum) the parameters shown in Table 3. Results are intended to assist in the eligibility assessment (e.g., assessment of potential renal disease), and will be retained in source documents but will not be entered in the eCRF.

Table 3Urine Dipstick

pН			
Glucose			
Ketones			
Bilirubin			
Blood			
WBC/Leukocyte Esterase.			

8.11 Pharmacokinetic Assessments

Instructions will be provided to sites with detailed information on sample collection, handling, and shipment requirements. All samples will be given a unique identifier. The exact clock time of dosing, date and time of last food intake, as well as actual sample collection date and time will be entered on the eCRF. The total volume of blood collected for pharmacokinetic assessments from each subject will be approximately 108 mL (7 tablespoons) over the course of the study.

8.11.1 PK Blood Collection and Processing

Blood Collection (plasma):

Blood samples will be collected and analyzed for omadacycline concentration at the following times:

- Day 1: within an hour prior to Dose 1, 1, 1.5, 2, 2.5, 3, 4, 6, 8, 12 hours (12 hour taken immediately before Dose 2);
 Dose 2 administered (times relative to Dose 1); 13, 13.5, 14, 14.5, 15, 16, 24 hours post dose
- Day 2: within an hour prior to dose, 1, 1.5, 2, 2.5, 3, 4, 6 hours
- Day 3: prior to the Day 3 dose
- EOT: anytime during the visit

8.11.2 Storing and Shipping of PK Samples

After all PK samples from a single subject have been collected and frozen at - 20° C or colder, the primary samples from each time point can be batched together and carefully packaged and shipped frozen at - 20° C or colder to the central laboratory designated by the sponsor. Samples are to be shipped with sufficient dry ice to remain frozen during overnight transit. For each subject and time point, the remaining stored aliquots will be retained on site at - 20° C or colder until released or requested by the sponsor.

8.12 Efficacy Assessments

8.12.1 Investigator's Assessment of Clinical Response

8.12.1.1 Investigator's Assessment of Clinical Response at EOT

EOT assessments should be performed on the calendar day of, or within 2 days following the last dose of any test article. If a subject withdraws prematurely or terminates participation in the study prior to completion of the planned antibiotic therapy, the EOT visit should be conducted.

The investigator will determine whether or not the subject meets the criteria of 1 of the following clinical outcomes:

Clinical Success: the subject is alive and the infection is sufficiently resolved such that further antibacterial therapy is not needed. These subjects may have some residual findings related to infection (ie, cough) requiring ancillary (ie, non-antibiotic) treatment (eg, expectorant). In order for the subject to be considered a Clinical Success at EOT, the subject may not meet any criteria for Clinical Failure or Indeterminate at EOT.

Clinical Failure: the subject requires alternative antibacterial treatment for CABP prior to EOT related to either (a) progression or development of new symptoms of CABP or (b) development of infectious complications of CABP (eg, empyema, lung abscess) or (c) subject developed an AE that required discontinuation of study therapy. Other reasons for Clinical Failure are:

- Subject is receiving antibacterial therapy that may be effective for the infection under study for a different infection from the 1 under study.
- Death prior to EOT visit.
- Other specified reason.

Indeterminate: the clinical response to test article could not be adequately inferred due to:

- Subjects were not seen for EOT evaluation because they withdrew consent, were lost to follow-up, other reason (specify).
- Other specified reason.

8.12.1.2 Investigator's Assessment of Clinical Response at PTE

The PTE assessment is to be performed 5 to 10 days after the subject's last day of therapy. The investigator will determine whether or not the subject meets the criteria of 1 of the following clinical outcomes:

Clinical Success: survival after completion of a test article regimen without receiving any systemic antibacterial therapy other than test article, resolution of signs and symptoms of the infection present at Screening with no new symptoms or complications attributable to CABP and no need for further antibacterial therapy.

Clinical Failure: the subject requires alternative antibacterial treatment for CABP prior to PTE related to either (a) progression or development of new symptoms of CABP or (b) development of infectious complications of CABP (eg, empyema, lung abscess).

- The subject is receiving antibiotics that may be effective for the infection under study for a different infection from the 1 under study.
- Death prior to PTE.
- Other specified reason.

Indeterminate: the clinical response to test article could not be adequately inferred due to:

- Subjects were not seen for PTE evaluation because they withdrew consent, were lost to follow-up, other (specify).
- Other specified reason.

8.12.2 Clinical Stability

The formal determination of the subject's Clinical Stability will be done programmatically using the investigator's assessment of the subject's vital signs entered into the eCRF. The investigator is not responsible for categorizing the subject's Clinical Stability. Clinical Stability will be determined daily and analyzed by day, EOT, and PTE.

Patients will be considered clinically stable if they achieve all of the following criteria:

- temperature $\leq 37.8^{\circ}C (100^{\circ}F);$
- heart rate ≤ 100 beats/minute;
- RR \leq 24 breaths/minute;
- systolic blood pressure \geq 90 mmHg; and
- arterial oxygen saturation $\ge 90\%$ or PaO2 ≥ 60 mmHg on room air.

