Efficacy Analyses: The number and percentage of subjects with investigator assessment of clinical response will be presented at each time point (EOT and PTE). The number and percentage of subjects who achieve clinical stability will be presented for each day, EOT and PTE.

Rationale for Number of Subjects: This study is designed to evaluate the PK profile of an oral dosing regimen, BID on Day 1 and QD on Day 2, in adults with CABP. The sample size determination is based on consideration of the precision of the estimate, GMR of $AUC_{(0-48)}$ for 300mg po to 100mg IV, derived from model-based simulations of omadacycline concentration data (Phase I studies).

With 20 evaluable subjects, there will be 90% probability that the 90% CIs of the GMR for $AUC_{(0-48)}$ will be within 80% and 125%. Up to 30 subjects will be enrolled so that at least 20 subjects are evaluable for bioavailability estimation. The number may be adjusted as needed to meet this requirement.

TABLE OF CONTENTS

SY	NOPSI	S	2
TA	BLE O	F CONTENTS	11
LIS	ST OF 7	ΓABLES	14
LIS	ST OF A	APPENDICES	14
LIS	ST OF A	ABBREVIATIONS AND DEFINITIONS OF TERMS	15
1	DISC	LOSURE STATEMENT	18
2	CON	TACTS	19
	2.1	Emergency Contacts	19
	2.2	Additional Contacts	19
3	INTR	ODUCTION	20
	3.1	Community Acquired Bacterial Pneumonia	20
	3.2	Omadacycline	20
4	STUI	DY OBJECTIVES	20
	4.1	Primary Objective	20
	4.2	Secondary Objectives	21
	4.3	Exploratory Objectives	21
5	INVE	STIGATIONAL PLAN	22
	5.1	Overall Study Description	22
	5.2	Rationale for Study Design	22
	5.3	Approximate Duration of Subject Participation	23
	5.4	Approximate Duration of Study	23
	5.5	Approximate Number of Subjects	23
6	STUI	DY POPULATION SELECTION	24
	6.1	Study Population	24
	6.2	Inclusion and Exclusion Criteria	24
	6.3	Screen Failures	27
7	STUI	DY TREATMENT(S)	28
	7.1	Treatments Administered	28
	7.2	Identity of the Investigational Product: Omadacycline	28
	7.3	Dose Selection Rationale	28
	7.4	Description of Treatments	29
	7.5	Test Article Administration	29
	7.5		
		7.5.1.1Management While on Oral Test Article	
	7.6	Dose Adjustments and Interruptions of Test Article	
	7.6	5 6	
	7.7	Dispensing Test Article	30

	7.8		and Concomitant Therapy	
	7.9		ibited Therapy	
	7.10		nitted Treatments	
	7.11		tment Compliance	
	7.12	Pack	aging and Labeling	31
	7.13	Stora	age and Accountability	31
	7.14	Inve	stigational Product Retention at Study Site	31
8	STU	DY Pl	ROCEDURES	32
	8.1	Info	med Consent	32
	8.2	Subj	ect Demographics/Other Baseline Characteristics	32

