7.7 Dispensing Test Article

Each study site will be supplied by the sponsor with the investigational product. The po test article will be supplied to the sites in wallets that contain active omadacycline tablets.

7.8 **Prior and Concomitant Therapy**

Treatments that have been administered within the 7 days prior to the date of informed consent, or during the Screening phase, will be recorded in the eCRF. The investigator is to instruct the subject to notify the study site about any new medications he/she takes after the start of the test article. All medications and significant non-drug therapies (including physical therapy and blood transfusions) administered after the subject starts treatment with test article must be listed in the eCRF (see Section 9). In addition, for antibacterial agents and anti-emetics administered 30 days prior to screening and concomitantly, the dose, unit, frequency and route must be entered in the eCRF.

7.9 **Prohibited Therapy**

All investigational medications or devices used during the 30 days prior to Screening are prohibited.

All of the following therapies are excluded starting from the time of consent through EOT visit:

- More than 24 hours (ie, a single dose of a daily therapy or the recommended daily frequency of a short acting therapy) of a potentially effective systemic antibacterial treatment within the 72 hours prior to the first dose of test article.
- Antacids and multivitamins containing multivalent cations (eg, aluminum, magnesium, calcium, bismuth, iron, or zinc) for 6 hours before and within 4 hours after oral doses.

7.10 **Permitted Treatments**

All other treatments not specified as prohibited are permitted during the study. Subjects requiring additional or alternative antibacterial therapy for their CABP will be judged as Clinical Failures and test article will be discontinued. Further treatment for their infection is at the discretion of the investigator or the subject's health care provider and will be considered as a concomitant medication.

Subjects should be encouraged to contact site personnel before starting any new treatment.

For all treatments received by the subject during the study, relevant information must be recorded on the subject's eCRF.

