8.20 Subject Discontinuation or Withdrawal

Reasons why a subject may discontinue or be withdrawn from the study include, but are not limited to, AE, lost to follow up, withdrawal by subject, physician decision, death, and other (specify reason eg, subject non-compliance or study termination by the sponsor). Subjects may voluntarily withdraw from the study for any reason at any time. Subjects are considered withdrawn from the study if they state an intention to withdraw, or fail to return for visits, or become lost to follow up for any other reason. If premature withdrawal from the study occurs for any reason, the investigator should determine the primary reason for a subject's premature withdrawal from the study and record this information on the eCRF.

Subjects who discontinue study treatment should not be considered withdrawn from the study (unless the subject withdraws informed consent). The date and primary reason for discontinuation of study treatment should be recorded. Subjects who discontinue study treatment prematurely should complete the EOT visit, PTE visit and Final Follow-up Assessment, if possible (see Schedule of Events - Appendix 1). The site should also collect subject safety information through the Final Follow-up assessment.

Site personnel should also contact the IxRS, if used to register the subject's discontinuation from test article.

For subjects who are lost to follow up, the investigator should show "due diligence" by documenting in the source documents steps taken to contact the subject, eg, dates of telephone calls, registered letters, etc.

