9.2 Clinical Stability

The formal determination of the subject's Clinical Stability will be done programmatically using the investigator's assessment of the subject's vital signs entered into the eCRF. The investigator is not responsible for categorizing the subject's Clinical Stability. Clinical Stability will be determined daily and analyzed by day, early clinical response window, EOT, and PTE.

Patients will be considered clinically stable if they achieve all the following criteria:

- temperature $\leq 37.8^{\circ}$ C (100°F);
- heart rate ≤ 100 beats/minute;
- RR \leq 24 breaths/minute;
- systolic blood pressure \geq 90 mmHg; and
- arterial oxygen saturation $\ge 90\%$ or PaO2 ≥ 60 mmHg on room air.

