9.3 Clinical Outcomes

The number and percentage of subjects classified as a Clinical Success, Clinical Failure, and Indeterminate by the Investigator's Assessment at EOT in the ITT population will be presented. The number and percentage of subjects in each response category for the overall assessment of Clinical response at PTE (based on the investigator's assessment) in the ITT population will also be presented. The number and percentage of subjects with stabilization of all vital signs associated with CABP at EOT will be presented for the ITT population as will the number and percentage of subjects with stabilization of each vital sign. These include temperature (no fever or hypothermia), SBP (> 90 mmHg), heart rate (< 90 bpm), RR (< 20 breaths/minutes), and PaO₂ (> 60 mmHg by pulse oximetry or ABG). WBC count (< 12,000 cells/mm³ or \geq 4,000 cells/mm³) and immature neutrophils (< 15%).

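### Clinical Stability is scored regardless of other antibacterial therapy, so a Clinical Failure who switched drug can count as clinically stable, mainly at PTE

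*Protocol*

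**What the plan says.** **How stability is scored.** Protocol 8.12.2: "The formal determination of the subject's Clinical Stability will be done programmatically using the investigator's assessment of the subject's vital signs entered into the eCRF". Categorising the subject is not the investigator's task. Five limits must all be met: temperature, heart rate, respiratory rate, systolic blood pressure, and oxygen saturation or PaO2 on room air. SAP 9.2 uses the same five. Neither section mentions other antibacterials, Clinical Failure or stopping test article.

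**When it is reported.** Protocol 8.12.2: "Clinical Stability will be determined daily and analyzed by day, EOT, and PTE". The synopsis agrees: "The number and percentage of subjects who achieve clinical stability will be presented for each day, EOT and PTE". SAP 9.2 adds one window: "Clinical Stability will be determined daily and analyzed by day, early clinical response window, EOT, and PTE". SAP 9.3 specifies a table at one visit: "The number and percentage of subjects with stabilization of all vital signs associated with CABP at EOT will be presented for the ITT population".

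**What happens to a subject who needs another drug.** Protocol 7.10: "Subjects requiring additional or alternative antibacterial therapy for their CABP will be judged as Clinical Failures and test article will be discontinued". Protocol 8.20: "Subjects who discontinue study treatment prematurely should complete the EOT visit, PTE visit and Final Follow-up Assessment, if possible". The Schedule of Events lists temperature, blood pressure, pulse oximetry, heart rate and respiratory rate at both EOT and PTE.

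**How the other efficacy measure treats it.** Clinical Success at PTE (Protocol 8.12.1.2) requires "survival after completion of a test article regimen without receiving any systemic antibacterial therapy other than test article". Counting an Indeterminate result as failure (Protocol 12.6.2, SAP 10.1) applies to Clinical Response only. All other variables fall under the observed-data rule in SAP 10.1.

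**The concern.** The exploratory objective (Protocol 4.3) is the efficacy of oral-only omadacycline, and Protocol 12.6.2 lists Clinical Stability among the key assessments that serve it. The algorithm reads physiology and not treatment. A subject whose pneumonia did not respond, who stopped omadacycline and then recovered on a replacement drug can meet all five limits at PTE. That subject is a Clinical Failure in one table and clinically stable in another, and nothing on the page tells the reader so.

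The trial has one arm, so no comparator offsets the effect. Stability figures also get used: Protocol 5.2 and 7.3 support the treatment duration with an earlier Phase 3 result that includes clinical stability by Day 7.

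A related gap is that no rule says how a subject who died, or who has no vital signs at the visit, counts for stability.

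**Working it through.** The documents state no rate, sample size or power for Clinical Stability, so there is no planned figure to reproduce. The check is of the rules, followed by simple arithmetic.

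**Step 1. Follow one switched subject through the rules.**

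- Needs another antibacterial for CABP: Clinical Failure, and test article stops (Protocol 7.10).
- The decision to stop prompts the EOT evaluation (Protocol 7.5.1.1). For a discontinued subject it is held that day (Protocol 9.3); the general window is the day of the last dose or the 2 days after it.
- PTE is 5 to 10 days after the last omadacycline dose (Protocol 9.4.1), and the subject attends if possible (Protocol 8.20).
- The program applies the five limits to the vital signs recorded at each visit. No text in either document makes this subject not stable or removes the subject. SAP Appendix 2 resolves uncertain antibacterial dates relative to EOT and PTE but does not link them to stability.

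So the two results can conflict at the same visit. There is little time to recover on another drug by EOT, but 5 to 10 days by PTE.

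**Step 2. Effect per subject.** Let k be the number of switched subjects who meet all five limits at PTE and N the denominator. Relative to scoring them as not stable, the percentage rises by 100 × k / N.

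- N = 30 (the enrolment ceiling, Protocol 5.5): 100 × 1/30 = 3.3 points each.
- N = 20 (the number intended to complete PK sampling, used here as a low denominator): 100 × 1/20 = 5.0 points each.

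**Step 3. Range.** Write k / N = r × s, with r the fraction switched and s the share of those who are stable at PTE. Neither is in the documents. I assume r = 5% to 15%. Because s cannot exceed 1, the rise is at most r, that is 5 to 15 points. In whole subjects:

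- N = 20: 1 to 3 subjects, 5.0 to 15.0 points.
- N = 30: 5% to 15% is 1.5 to 4.5 subjects. The whole counts inside that range are 2 to 4, or 6.7 to 13.3 points.

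**Step 4. Illustration**, with every unswitched subject assumed stable (the difference does not depend on this):

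| N | Switched | Share of switched stable at PTE | As written | Switched scored not stable | Difference |
|---|---|---|---|---|---|
| 30 | 3 | all | 100.0% | 90.0% | 10.0 |
| 30 | 3 | half, on average | 95.0% | 90.0% | 5.0 |
| 20 | 3 | all | 100.0% | 85.0% | 15.0 |
| 20 | 3 | half, on average | 92.5% | 85.0% | 7.5 |

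**Step 5. Denominator.** SAP 9.3 names the ITT population for vital-sign stabilisation at EOT but does not say how a missing vital sign counts. For stability at PTE and by day, no denominator is stated.

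**The case against.** The strongest reply is that the plan already has an efficacy answer that deals with switching. Protocol 12.6.2 defines the efficacy outcome as the investigator's Clinical Response in the ITT population, and there a switch for CABP is a failure. Stability describes physiological state, and reporting it whatever the treatment is a legitimate choice. No formal comparisons are planned (Protocol 12.8) and no decision hangs on the figure. All data are listed, so in about 30 subjects a switched but stable case can be found by hand. This stands, and it is why the point is minor. It does not close the gap, because neither document says that the figure is meant to be regardless of other therapy.

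The reply also disposes of several stronger readings that a reader might infer:

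- *That EOT is affected as much as PTE.* The rules do not prevent it, but EOT is prompted by stopping and falls 0 to 2 days after the last dose, and a subject stopped for progression is unlikely to meet five limits that soon.
- *That the bias can only be upward.* Counting switched subjects can only raise the percentage above the adjusted one. It does not follow that all of the rise is error. Clinical Failure at EOT includes a switch because an adverse event ended study therapy (Protocol 8.12.1.1, item c). Someone who stabilised on omadacycline and then switched for that reason was stable on omadacycline, and the adjusted row would understate that.
- *That the overstatement could reach 17 points.* This needs 5 of 30 subjects (16.7%), above the assumed 15%.
- *That subjects without vital signs drop out at EOT.* SAP 9.3 already names the ITT population there. What is open is how missing values count, and which denominator applies at PTE and by day.

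**Conclusion.** The point holds in limited form. As written, Clinical Stability is regardless of other antibacterial therapy without saying so. A subject who switched drug for CABP and is a Clinical Failure can be counted as clinically stable, mainly at PTE. That can overstate stability as evidence for oral-only omadacycline and is inconsistent with the Clinical Response rule.

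The size is 3.3 points per such subject at n = 30 or 5 points at n = 20. At an assumed 5% to 15% switched, the overstatement is at most about 5 to 15 points. The upper end requires every switched subject to attend PTE, to meet all five limits, and to owe that to the other drug. It is smaller where some were stable before the switch.

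A reader might go further and infer that the trial's efficacy result, or the trial itself, is compromised. The documents do not support that: the primary PK conclusion does not use stability, and Clinical Response already counts these subjects as failures. Severity: minor, confined to an exploratory, descriptive endpoint.

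**What to change.** In SAP 9.2 and 9.3, before database freeze:

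1. Add an adjusted stability row at PTE, and at any other assessment after a switch. Score as not stable any subject who, since the first dose of test article, has received a non-study systemic antibacterial potentially effective for CABP. This matches Clinical Response, whose failure criteria also cover such a drug given for a different infection. Counting only from the first dose keeps permitted pre-study antibacterials from triggering the rule.
2. Use the ITT denominator at EOT and PTE, with deaths and missing vital signs scored as not stable.
3. Keep the vital-signs-only row beside it, labelled *regardless of other antibacterial therapy*.
4. Flag switches made because of an adverse event, so that a reader can see how many may have stabilised first.

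While editing, reconcile the vital-sign cut-offs. SAP 9.3 uses heart rate below 90 and respiratory rate below 20, where SAP 9.2 uses at most 100 and at most 24. That is a separate inconsistency, but it affects the same tables.

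The cost is a few lines of text and programming. Start and stop times of concomitant antibiotics are already collected (Schedule of Events, note k), and SAP Appendix 2 already handles uncertain antibacterial dates. The downside is a slightly less favourable percentage, and subjects who switched for an adverse event after stabilising count as not stable in the adjusted row. The second row and the flag make that visible.
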